2.5.2 Statistical hypothesis, model, and method of analysis

The analysis will be mainly based on summary statistics and no inferential statistical analysis is planned. The graphical summaries on PK concentration will also be provided.

2.5.3 Handling of intercurrent events

All PK data will be presented as recorded in the descriptive statistics. For participants who discontinue from study or death where PK information is not available, the impact of this on the interpretation of the results will be considered. Additional summaries as needed to support this interpretation may be presented. It is not intended to impute missing data after discontinuation.

2.5.4 Handling of missing values not related to intercurrent event

Missing primary endpoint values due to protocol deviations or other issues related to a pandemic are not anticipated as measures have been put in place, where possible, to allow for the protocol assessments to be conducted. In case missing values do occur for such reasons, only data available will be used.

2.5.5 Sensitivity analyses for primary endpoint/estimand

No sensitivity analyses are planned.

2.5.6 Supplementary analyses

In case PK profiles in patients are very different from those in healthy volunteers (HV), the PK profiles may be assessed using a population PK model to confirm dosing regimens that provide comparable exposure in patients as observed in HV. This analysis would be reported separately and is planned in a separate analysis plan.

2.5.7 Supportive analyses

No subgroup or supportive analyses are planned.

2.6 Analysis supporting secondary endpoints/estimands

The analysis for secondary endpoints will be based on descriptive statistics by treatment group.

2.6.1 Secondary endpoints/secondary estimands

For all safety analyses, the safety set will be used. All summaries where appropriate (e.g. change from baseline summaries), listings and tables will be presented by treatment group.

Adverse events

All information obtained on adverse events will be displayed by treatment group and participant.

The number (and percentage) of participants with treatment emergent adverse events (events started after the first dose of study medication or events present prior to start of participant and investigator-blind treatment but increased in severity based on preferred term) will be summarized in the following ways:

- by treatment, primary system organ class and preferred term.
- by treatment, primary system organ class, preferred term and maximum severity.

Separate summaries will be provided for study medication related adverse events, death, serious adverse events, other significant adverse events leading to discontinuation.

The number (and proportion) of participants with following adverse events of special interest/related to potential risks will be summarized by treatment:

- bleeding
- perivascular/vascular mineralization
- infusion reaction and hypersensitivity
- anti-drug antibody mediated reactions (immunogenicity).

A participant with multiple adverse events within a primary system organ class is only counted once towards the total of the primary system organ class.

The following adverse events will be counted during 90-day study period:

- These events are those with an onset after the start of the treatment period, or which were present prior to the start of the treatment period but increased in severity, changed from being not suspected to being suspected of study treatment relationship, or developed into SAEs after the start of the treatment period.

Vital signs

Summary statistics will be provided for all vital signs data by treatment and visit/time. Where ranges are available, abnormalities (and relevant orthostatic changes) will be listed by treatment group, participant, and visit/time. If appropriate, summary statistics of the occurrence of abnormalities may be provided by treatment.

Graph of mean arterial pressure (MAP) over time will be provided by treatment. Of note MAP is defined as diastolic blood pressure + 1/3*pulse pressure, where pulse pressure =systolic blood pressure – diastolic blood pressure).

Clinical laboratory evaluations

Summary statistics for all laboratory data will be provided by treatment and visit/time. Shift tables using the low/normal/high/ (low and high) classification may be used, as appropriate, to compare baseline to the worst value. Where normal ranges are available, abnormalities in laboratory data will be listed by treatment group, participant, and visit/time.

Graphical displays of selected safety parameters (e.g. hematological parameters, thyroid and reproductive hormone levels) over time will be provided by treatment group.

For laboratory parameters which are lower or greater than the limit of quantification, the number and percentage of values below the lower limit of quantification (LLOQ) and above the upper limit of quantification (ULOQ) will be presented for categorical variables. For numerical presentation, the values less than LLOQ will be imputed as a value of $0.5 \times \text{LLOQ}$ and the values greater than ULOQ will be imputed as a value of $1.5 \times \text{ULOQ}$.

The frequency and percentage of participants with clinically significant abnormal laboratory values shown in [Table 2-2](#) will also be provided.

Table 2-2 **Clinically notable laboratory values**

Parameter	Conventional Alert Value	Conventional Units	SI Alert Value	SI Units
Hematology				
Red Blood Cell Count	>50% increase, >30% decrease	$\times 10^6/\mu\text{L}$	>50% increase, >30% decrease	$\times 10^{12}/\text{L}$
Hemoglobin	>50% increase, 30% decrease, or any value <7	g/dL	>50% increase, >30% decrease, or any value <70	g/L
Hematocrit	>50% increase, >30% decrease	%	>50% increase, >30% decrease	L/L
White Blood Cell Count	>50% increase, >50% decrease	$\times 10^3/\mu\text{L}$	>50% increase, >50% decrease	$\times 10^9/\text{L}$
Platelet Count	>75% increase, >50% decrease	$\times 10^3/\mu\text{L}$	>75% increase, >50% decrease	$\times 10^9/\text{L}$
Chemistry				
BUN	>50% increase	mg/dL	>50% increase	mmol/L
Creatinine	>50% increase	mg/dL	>50% increase	$\mu\text{mol}/\text{L}$
Albumin	<2	g/dL	<20	g/L
Glucose	>50% increase, >50% decrease, or any value <60	mg/dL	>50% increase, >50% decrease, or any value <3.3	mmol/L
Total Bilirubin	>100% increase	mg/dL	>100% increase	$\mu\text{mol}/\text{L}$
Creatine phosphokinase (CPK)	>300% increase	U/L	>300% increase	U/L
AST (SGOT)	>150% increase	U/L	>150% increase	U/L
ALT (SGPT)	>150% increase	U/L	>150% increase	U/L
Alkaline phosphatase	>100% increase	U/L	>100% increase	U/L
Sodium	>5% increase, or any value >150	mEq/L	>5% increase, or any value >150	mmol/L
Potassium	>20% increase, >20% decrease, or any value >5.3	mEq/L	>20% increase, >20% decrease, or any value >5.3	mmol/L

Parameter	Conventional Alert Value	Conventional Units	SI Alert Value	SI Units
Chloride	>10% increase, >10% decrease	mEq/L	>10% increase, >10% decrease	mmol/L
Calcium	>10% increase, >10% decrease	mg/dL	>10% increase, >10% decrease	mmol/L
Uric Acid	>50% increase	mg/dL	>50% increase	mmol/L

Immunogenicity

All immunogenicity results will be listed by treatment group, subject and visit/time. The listing will contain ADA status (negative or positive) and for ADA-positive samples a titer and ADA neutralization potential of TIN816 and/or endogenous CD39. Subjects with one or more treatment emergent (induced or boosted) ADAs are counted as ADA-positive subjects and they will be summarized by treatment arm to derive an ADA incidence. Incidences for neutralizing ADAs will be assessed as well, if appropriate. Visualizations overlaying ADA status including characterizations, along with PK concentration and potentially efficacy read-outs, will be presented.

Deaths

The number of deaths resulting from treatment-emergent AEs will be summarized by SOC and PT. Death refers to treatment-emergent adverse events with fatal outcome. In addition, a separate summary of death events including on treatment and post treatment deaths will be provided if appropriate.

All the deaths in the clinical database will be listed.

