10.3 Appendix 3: Clinical laboratory tests

10.3.1 Clinically notable laboratory values and vital signs

Clinically significant abnormal laboratory values or test results must be identified through a review of values outside of normal ranges/clinically notable ranges, significant changes from baseline or the previous visit.

Table 10-1 Clinically notable laboratory values

Parameter	Conventional Alert Value	Conventional Units	SI Alert Value	SI Units
Hematology				
Red Blood Cell Count	>50% increase, >30% decrease	$\times 10^6/\mu\text{L}$	>50% increase, >30% decrease	$\times 10^{12}/\text{L}$
Hemoglobin	>50% increase, 30% decrease, or any value <7	g/dL	>50% increase, >30% decrease, or any value <70	g/L
Hematocrit	>50% increase, >30% decrease	%	>50% increase, >30% decrease	L/L
White Blood Cell Count	>50% increase, >50% decrease	$\times 10^3/\mu\text{L}$	>50% increase, >50% decrease	$\times 10^9/\text{L}$
Platelet Count	>75% increase, >50% decrease	$\times 10^3/\mu\text{L}$	>75% increase, >50% decrease	$\times 10^9/\text{L}$
Chemistry				
BUN	>50% increase	mg/dL	>50% increase	mmol/L
Creatinine	>50% increase	mg/dL	>50% increase	$\mu\text{mol}/\text{L}$
Albumin	<2	g/dL	<20	g/L
Glucose	>50% increase, >50% decrease, or any value <60	mg/dL	>50% increase, >50% decrease, or any value <3.3	mmol/L
Total Bilirubin	>100% increase	mg/dL	>100% increase	$\mu\text{mol}/\text{L}$
Creatine phosphokinase (CPK)	>300% increase	U/L	>300% increase	U/L
AST (SGOT)	>150% increase	U/L	>150% increase	U/L
ALT (SGPT)	>150% increase	U/L	>150% increase	U/L
Alkaline phosphatase	>100% increase	U/L	>100% increase	U/L
Sodium	>5% increase, or any value >150	mEq/L	>5% increase, or any value >150	mmol/L
Potassium	>20% increase, >20%	mEq/L	>20% increase, >20%	mmol/L

Parameter	Conventional Alert Value	Conventional Units	SI Alert Value	SI Units
	decrease, or any value >5.3		decrease, or any value >5.3	
Chloride	>10% increase, >10% decrease	mEq/L	>10% increase, >10% decrease	mmol/L
Calcium	>10% increase, >10% decrease	mg/dL	>10% increase, >10% decrease	mmol/L
Uric Acid	>50% increase	mg/dL	>50% increase	mmol/L

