2.1.1 General definitions

The term “**study treatment**” and/or “**study drug**” refers to the 2-hour study infusion drug during the study, that is TIN816 2 mg/kg.

For analysis purposes, “**Baseline**” is defined to be the last result obtained at or prior to start of study treatment (Day 1) for baseline demographics, medical history, lab values, vital signs and ECGs. Most variables will have their baseline at Day 1, unless otherwise specified. For assessments not performed at Day 1, the assessment at the screening visit or most recent assessment prior to start of study treatment will be used as baseline.

The reference creatinine baseline is defined as below.

For hospital-acquired AKI, a stable serum creatinine obtained in the hospital prior to AKI should be used as reference baseline, otherwise, baseline serum creatinine in the following order of preference:

1. Median value within 3 months of the hospital admission. If not available:
2. Median value between 3 and 6 months prior to hospital admission. If not available:
3. At hospital admission.

“Post-Baseline” is defined for analysis purposes to be any value collected after the “baseline” as defined above for analysis purposes.

The term **“study day”** is defined relative to the analysis reference date, which is the date of first administration of study treatment.

The *study day* for a scheduled or unscheduled visit on or after the analysis reference date is defined as:

Study day = (Date of Visit) – (analysis reference date) +1.

The *study day* for a scheduled or unscheduled visit before the analysis reference date is defined as:

Study day = (Date of visit) – (analysis reference date).

Thus the analysis reference date (date of first administration of study treatment) will be study day 1 and the date directly prior the analysis reference date will be study day □1 (there is no study day 0).

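### For 10 of 19 laboratory parameters, SAP Table 2-2 can count a return to normal after sepsis as a clinically significant abnormality

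*SAP*

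**What the plan says.** SAP 2.6.1 (Clinical laboratory evaluations) promises, by treatment group: "The frequency and percentage of participants with clinically significant abnormal laboratory values shown in" Table 2-2. That table repeats Protocol Table 10-1. Typical lines are ">75% increase, >50% decrease" for platelets, ">50% increase, >50% decrease, or any value <60" for glucose and ">5% increase, or any value >150" for sodium.

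The table does not say what the percentages are measured against. SAP 2.1.1 supplies a general rule: baseline "is defined to be the last result obtained at or prior to start of study treatment (Day 1) for baseline demographics", in a list that goes on to include laboratory values. The same section defines a second baseline for creatinine: for hospital-acquired AKI, "a stable serum creatinine obtained in the hospital prior to AKI should be used as reference baseline". Protocol 10.3.1, which introduces the parent table, says that significant results "must be identified through a review of values outside of normal ranges/clinically notable ranges, significant changes from baseline or the previous visit".

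SAP 2.1.1 also places summaries of notable laboratory abnormalities among the analyses that use every post-baseline value, unscheduled visits included. Protocol 8.4 schedules hematology and chemistry after dosing at Days 5, 14, 30 and 90.

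The other laboratory displays in SAP 2.6.1 are summaries by visit, a listing of values outside normal ranges where ranges exist, and low/normal/high shift tables that are optional.

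**The concern.** In the protocol, these lines are alert values that prompt a review. In the SAP, meeting a line is itself the outcome, and every hit is labelled clinically significant and abnormal.

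That label is unsafe when the starting value is the abnormal one. Participants are dosed with sepsis, a SOFA score of at least 2 outside the renal component, and AKI. The counting window then runs to Day 90, so it covers convalescence. A white count falling from a septic peak, or platelets rising from a septic trough, can cross a percent line because the patient is getting better.

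Safety laboratory parameters against placebo are a named secondary endpoint. For the affected analytes the count mixes harm with recovery, and a difference between arms cannot be read as a safety difference. Calcium, which is monitored because of the mineralization event of special interest, is one of them.

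**Working it through.** The plan states no expected frequency for this table, so there is no figure to reproduce. The check has three parts: classify the lines, apply them to worked values, and test the remedy.

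**1. Classify the 19 parameters in Table 2-2.**
- Percent change only: 14.
- Percent change or an absolute cut: 4 (hemoglobin <7, glucose <60, sodium >150, potassium >5.3).
- Absolute only: 1 (albumin <2).
- With a percent line: 14 + 4 = 18. With a reference-range condition on that line: 0. The absolute cuts are joined by *or*, so they add hits and never remove one.
- Percent line in both directions: 9 (RBC, hemoglobin, hematocrit, WBC, platelets, glucose, potassium, chloride, calcium). Sodium flags rises, which is the recovery direction from a low value. Total open to miscounted recovery: 9 + 1 = 10.
- Increase-only, with recovery being a fall: 8 (BUN, creatinine, bilirubin, CPK, AST, ALT, ALP, uric acid). Check: 10 + 8 + 1 = 19.

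**2. Apply the lines.** Change = 100 × (later − baseline) / baseline. The values are constructed. They are judged on the protocol's own SOFA and APACHE-II tables where possible, otherwise on an assumed ordinary adult range.

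| Parameter | Baseline to later | Change | Line met | Meaning |
|---|---|---|---|---|
| WBC | 25 to 10 | -60.0% | >50% fall | APACHE-II points 2 to 0 |
| Platelets | 100 to 180 | +80.0% | >75% rise | SOFA points 1 to 0 |
| Sodium | 128 to 135 | +5.5% | >5% rise | APACHE-II points 2 to 0 |
| Potassium | 3.0 to 3.7 | +23.3% | >20% rise | APACHE-II points 1 to 0 |
| Glucose (mg/dL) | 220 to 105 | -52.3% | >50% fall | falling from high (range assumed) |
| Calcium (mg/dL) | 7.6 to 8.6 | +13.2% | >10% rise | low to normal (range assumed) |
| ALT (× ULN) | 0.35 to 0.90 | +157.1% | >150% rise | never above normal |

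All seven are counted. The first six are recoveries. ALT shows the lesser fault in the increase-only lines: a rise inside the normal range is counted. True recovery on those lines is not counted: creatinine 4.0 to 2.0 (-50.0%) and bilirubin 6 to 1 (-83.3%) meet no line.

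**3. Comparator.** Creatinine 4.1 is 100 × (4.1 − 2.8)/2.8 = +46.4% from a Day 1 value of 2.8, which is not counted. Against a pre-AKI reference of 1.0 it is +310%, which is counted. The result depends on which of the two SAP 2.1.1 baselines is used.

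**4. Weight of one count.** About 20 participants at 3:1 gives 15 and 5. One participant is 1/5 = 20 points on placebo and 1/15 = 6.7 points on TIN816.

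**5. Test the remedy.** Suppose a percent line counts only if the later value is also outside the local range in the direction of the change. On the assumed ranges, none of the seven rows qualifies: WBC 10 and glucose 105 are not low, and the other five are not high. The count goes from 7 of 7 to 0 of 7.

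**The case against.** The strongest reply is that this is one descriptive display among several, that no decision rule uses it, and that the examples are constructed. By-visit summaries and a range-based listing are committed, laboratory AEs are assessed on clinical grounds, and mineralization is summarized as an AE of special interest rather than from the calcium line. All of that stands and limits the impact. It does not correct the count: by-visit summaries do not count participants, a listing gives no frequency, and the shift tables may never be produced.

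A reader might infer more than the documents support:

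- *That the whole table is reversed.* It is not. Eight parameters flag only rises where recovery is a fall, and albumin is absolute only.
- *That the percentages are certainly taken from the septic baseline.* SAP 2.1.1 points that way, but Table 2-2 names no comparator, and Protocol 10.3.1 allows "values outside of normal ranges/clinically notable ranges, significant changes from baseline or the previous visit".
- *That deterioration is systematically missed.* Most such examples, like platelets 180 to 95 (-47.2%) or creatinine +46.4%, fall just short of a cut, as happens with any threshold. A 25-49% creatinine rise, if confirmed, has its own tier in Protocol Table 10-5. The one structural gap is sodium, which has no decrease line: 140 to 118 (-15.7%) meets nothing.
- *That pre-dose values are themselves counted.* The count uses post-baseline values. An absolute line can be met by a value that was already beyond the cut before dosing, such as albumin 1.9 and unchanged, but only through the later result.

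It is also tempting to drop any absolute line already met at baseline. That would hide worsening that is now counted: potassium 5.5 to 6.55 (+19.1%, under the 20% line), hemoglobin 6.9 to 5.0 (-27.5%, under the 30% line), and albumin 1.9 to 1.2, which has no percent line at all.

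**Conclusion.** The concern holds for ten of the 19 parameters. If Table 2-2 is followed as written, with the SAP 2.1.1 pre-dose baseline, recovery can enter a table labelled as clinically significant abnormality. For the eight increase-only lines the fault is narrower: a rise within normal limits can be flagged.

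The effect is on the reading of a secondary safety table in about 15 versus 5 participants, where a single recovery can move the placebo percentage by 20 points. The primary PK analysis is unaffected. How often this will happen cannot be computed from the documents, so the statement that a faster-recovering arm will look worse is a possibility and not a prediction.

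The conclusion assumes that the SAP's general laboratory baseline is the comparator, and that some participants have abnormal values of these analytes at dosing, as the entry criteria make likely. The glucose and calcium examples also rest on assumed reference ranges.

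**What to change.** Change the SAP tabulation only; the investigator alerts in Protocol Table 10-1 can stay as they are. In SAP 2.6.1:

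- Name the SAP 2.1.1 pre-dose baseline as the comparator for Table 2-2, and state which creatinine baseline applies.
- Count a percent-change line only when the post-baseline value is also outside the local reference range in the direction of the change. Say how values without a local range are handled.
- Show increases and decreases in separate rows.
- Keep all other percent-change hits in the listing.
- Keep counting the absolute lines on post-baseline values, but show separately the participants who already met the line at baseline. Do not remove them, so that further worsening stays visible.
- Note that sodium has no decrease line, and commit to the low/normal/high shift tables. Shifts from normal to low sodium are then tabulated without setting a new cut-off.

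The cost is SAP wording and modest programming. The ranges are already needed for the committed abnormality listing. The downside is that large shifts inside the normal range, such as platelets 390 to 185 (-52.6%), move from the table to the listing; with bleeding an event of special interest, that listing should be read for platelets. The SAP table will also differ from Protocol Table 10-1, which should be recorded in SAP section 4.

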4.2 Scientific rationale for study design

This study is designed as a multi-center, participant and investigator-blinded, randomized, placebo-controlled study to evaluate the PK/PD profile as well as the safety and efficacy of TIN 816 in patients with SA-AKI. The participant and investigator-blinded design is to control for bias in the assessment of safety, efficacy [REDACTED]. The study design fulfills the purpose of the trial in the assessment of pharmacokinetics in SA-AKI patients, collecting preliminary safety and efficacy data while obtaining operational insights in the acute trial setting. The data generated from this study will be used to support further development of TIN816 for the indication of SA-AKI.

Potential study participants will consist of patients with a recent diagnosis of sepsis (according to the criteria defined by The Third International Consensus Definition for Sepsis and Septic Shock (Sepsis-3) with an additional diagnosis of AKI (stage 1 or greater using the KDIGO serum creatinine-based criteria). The patient population is typical for the intended indication without a further enrichment. In addition, patient safety is well considered in the design of inclusion /exclusion criteria.

The primary objective of this study is to evaluate the PK profile in SA-AKI patients. PK sampling schedule and PK parameters including C_{max} , T_{max} , $T_{1/2}$, Cl , V_z , AUC_{last} and AUC_{inf} are considered as standard for PK assessments.

[REDACTED]

The study includes safety and efficacy endpoints. Safety will be monitored during the entire course of the study. All adverse event (AE) and serious adverse event (SAE) will be collected and reported following standard processes and local regulations.

Although this study is not powered for evaluation of efficacy of TIN816, inclusion of those efficacy endpoints will help to gain important insights in future phase 2 study design and key clinical data collection.

AKI develops in 40-60% patients with sepsis and progresses during the first few weeks resulting in a reduction in GFR. RRT is often required either temporarily or permanently and morbidity and mortality are high because of the multiple organs affected. Thus, selection of the efficacy endpoints for this patient population aims to assess the presence and severity of the complications of SA-AKI and the potential benefit of TIN816.

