8.3.3 Kidney disease improving global outcomes (KDIGO) stage

Determination of severe AKI will be grounded in the staging system outlined in the KDIGO Guidelines for acute kidney injury. This classification system stages AKI into three levels based on the extent of sCr elevation in parallel with the degree and duration of oliguria; patients are classified based on the worst finding (either sCr or oliguria). Three stages of AKI are classified in the table below:

Table 8-1 Staging of AKI

Stage	Serum creatinine	Urine output
1	1.5-1.9 times baseline OR ≥ 0.3 mg/dl (≥ 26.5 μ mol/l) increase	<0.5 ml/kg/h for 6-12 hours
2	2.0-2.9 times baseline	<0.5 ml/kg/h for ≥ 12 hours
3	3.0 times baseline OR Increase in serum creatinine to ≥ 4.0 mg/dl (≥ 353.6 μ mol/l) OR Initiation of renal replacement therapy	<0.3 ml/kg/h for ≥ 24 hours OR Anuria for ≥ 12 hours

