8.3.4 Renal replacement therapy (RRT)

Initiation of RRT: RRT should be initiated as per local protocol but recommended based on the criteria described by [Bellomo et al \(2012\)](#). Meeting at least one criterion of the below makes the patient eligible for initiation of RRT:

1. Anuria (negligible urine output for 6 hours)
2. Severe oliguria (urine output < 200 mL over 12 hours)
3. Hyperkalemia (potassium concentrations > 6.5 mmol/L)
4. Severe metabolic acidosis ($pH < 7.2$ despite normal or low partial pressure of carbon dioxide in arterial blood)
5. Volume overload
6. Pronounced azotemia (urea concentrations > 30 mmol/L (> 84 mg/dL) or creatinine concentrations > 300 μ mol/L (> 3.4 mg/dL))
7. Clinical complications of uremia (e.g., encephalopathy, pericarditis, neuropathy)

Timing of termination of RRT: RRT should be terminated as per local protocol but is recommended based on criteria as used in the Veterans Affairs/National Institutes of Health (VA/NIH) Acute Renal Failure Trial Network Study ([Palevsky et al., 2008](#)). If diuresis > 30

mL/hour and there are no other indications for RRT, then endogenous creatinine clearance should be calculated using a 6-hour urine collection period. If endogenous creatinine clearance ≥ 20 mL/min, RRT should be discontinued. If endogenous creatinine clearance ≤ 12 mL/min, RRT should be continued. However, although the criteria for starting and stopping mentioned above are strongly preferred within the protocol setting, based on clinical judgment investigators may deviate from these criteria.

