The term **“unscheduled visit”** refers to visits that occurred not as part of the Clinical Trial Protocol assessment schedule. Data collected at unscheduled visits will, in general, not be used in ‘by-visit tabulations’ or graphs, but they will be included in analyses of safety parameters based on all post-baseline values such as summary statistics of clinically notable abnormalities of laboratory data. For efficacy evaluations, measurements from unscheduled visits will generally not be used, unless where otherwise specified. All data collected at both scheduled and unscheduled visits will be included in data listings.

“Completion”: a participant will be considered to have completed the study when the patient has completed the Day 90 visit in the study or End of Study (EOS) for participants who discontinue from the study. The maximum of the date of last visit in the randomized treatment period, date of withdrawal of consent (in case of withdrawal from study), would be the date of **last contact** for the patient in the study.

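### The SAP 2.6.1 laboratory tables take no account of renal replacement therapy started after dosing, so the creatinine and BUN counts can miss participants who go onto it

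*SAP*

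**What the plan says.** The laboratory part of SAP Section 2.6.1 plans three kinds of output:

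- By-visit tables: "Summary statistics for all laboratory data will be provided by treatment and visit/time".
- Shift tables, which are optional and would be used "as appropriate, to compare baseline to the worst value".
- Notable-value counts: "The frequency and percentage of participants with clinically significant abnormal laboratory values shown in" Table 2-2. Creatinine and BUN each have one alert there, a rise of more than 50%, with no absolute limit. Potassium has a wider one: ">20% increase, >20% decrease, or any value >5.3".

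The section has rules for results outside the limits of quantification. It has none for results taken on RRT. Sections 2.6.2 and 2.6.3 are marked not applicable, and 2.7 refers back to 2.6. In the visible SAP analysis text, RRT appears only as a yes/no item among the screening characteristics (2.3.1). Protocol Section 9.4.2 has no rule either.

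The protocol expects RRT after entry. Section 4.2 says that "RRT is often required either temporarily or permanently and morbidity and mortality are high because of the multiple organs affected". Section 8.3.4 lists seven recommended criteria: "Meeting at least one criterion of the below makes the patient eligible for initiation of RRT". Table 8-1 in Section 8.3.3 puts "Initiation of renal replacement therapy" in stage 3 as an alternative to the creatinine thresholds.

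**The concern.** RRT removes creatinine, urea and potassium, so a value taken on RRT reflects the treatment as well as the kidney. Two outputs are exposed. A participant whose creatinine or BUN has not risen by more than 50% before RRT starts may never do so afterwards, and then does not appear in that count. In the by-visit tables, values lowered by RRT are averaged with values that reflect native kidney function.

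Laboratory safety is part of the secondary endpoint. Protocol Section 2.3.2.2 names mineralization in the minipig kidney as a potential risk and cites unchanged kidney markers in healthy volunteers as reassurance. A reader looking for renal harm will turn to these tables. If the arms differ in RRT use, the arm with more of it could look better than it is.

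**Working it through.** The plan gives no figure on this point. Its only sample-size figures concern PK precision and do not enter here.

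**Inputs from the documents**

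- Creatinine and BUN alert: more than 50% above baseline (SAP Table 2-2).
- Laboratory baseline: the last value up to the start of dosing on Day 1 (SAP 2.1.1). AKI is already present by then (Protocol 5.1, criterion 5).
- Azotemia criterion for RRT: creatinine above 3.4 mg/dL (300 µmol/L) or urea above 84 mg/dL (30 mmol/L) (Protocol 8.3.4). Since 84/30 = 2.8, the conversion factor for urea nitrogen, I read the 84 mg/dL as BUN.
- Potassium criterion for RRT: above 6.5 mmol/L (same section).
- Planned numbers: about 15 TIN816 and 5 placebo.

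**Step 1: when RRT comes before the creatinine or BUN alert.** A value at the criterion exceeds a 50% rise only if baseline is below criterion/1.5.

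- Creatinine: 3.4/1.5 = 2.27 mg/dL (300/1.5 = 200 µmol/L).
- BUN: 84/1.5 = 56 mg/dL (urea 30/1.5 = 20 mmol/L).

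| Day 1 creatinine (mg/dL) | Rise on reaching 3.4 | Alert |
|---|---|---|
| 2.0 | 3.4/2.0 − 1 = 70% | yes |
| 2.5 | 3.4/2.5 − 1 = 36% | no |
| 3.0 | 3.4/3.0 − 1 = 13% | no |

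Entry criteria do not rule out the last two rows. The creatinine example in exclusion 8 is above 4 mg/dL on admission. RRT started for anuria, oliguria, acidosis or volume overload need not come with either alert, whatever the baseline.

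**Step 2: potassium.** A recorded value above 6.5 exceeds 5.3 and is always flagged. A fall from 5.3 to 4.0 is (4.0 − 5.3)/5.3 = −25% and is flagged as a decrease. The potassium count therefore does not hide these participants. The by-visit potassium summary is still affected.

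**Step 3: weight of one participant.** 1/15 = 6.7 percentage points on TIN816; 1/5 = 20 points on placebo.

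**Step 4: by-visit mean (assumed values).** The documents give no RRT rate. At 10% to 40%, 0.1 × 15 = 1.5 to 0.4 × 15 = 6 TIN816 participants and 0.5 to 2 placebo participants would be on RRT. Suppose creatinine is 2.0 mg/dL on RRT and would have been 4.0 without it, with all of them on RRT at that visit. The mean is then lower by share × (4.0 − 2.0), which is 0.2 to 0.8 mg/dL.

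**Step 5: does dropping on-RRT values cure this?** Not alone. Suppose 3 of 15 are on RRT at 2.0 mg/dL and the other 12 average 1.8. The full mean is (3 × 2.0 + 12 × 1.8)/15 = 1.84. Without the three it is 1.80, which looks slightly better still, because the sickest have been removed.

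**The case against.** The strongest reply is that the plan already catches most of this.

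- Unscheduled results enter "analyses of safety parameters based on all post-baseline values such as summary statistics of clinically notable abnormalities of laboratory data", and shift tables, if produced, use the worst value. One recorded peak before RRT is enough. Central creatinine is drawn at every visit from baseline, including Days 2, 3, 5, 8 and 11, so early creatinine peaks will often be on record.
- Laboratory abnormalities that need treatment are adverse events (Protocol 8.6.1). Treatment-emergent events, SAEs and deaths are tabulated separately.
- SAP text between 2.7 and 2.11 is not visible. LOCF and eGFR are among the SAP abbreviations, and RRT sits under the protocol's efficacy assessments, so an RRT rule for other endpoints may exist.
- The 2.27 and 56 mg/dL figures require Day 1 as baseline and RRT starting at the criterion. Section 8.3.4 defers to local practice and lets investigators deviate. Table 2-2 names no baseline. From an assumed pre-AKI reference of 1.5 mg/dL, a value of 3.4 is a 127% rise and is flagged.
- Everything is descriptive, in about 20 participants.

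All of this stands as a limit on the point, but none of it supplies the missing rule. Scheduled local chemistry after Day 1 falls only on Days 5, 14, 30 and 90 (Protocol 8.4), and by-visit tables generally leave out unscheduled values, so BUN and potassium peaks between visits can be absent from them. No adverse event of special interest is renal. AKI present at consent is medical history and becomes treatment-emergent only if it worsens, becomes serious or is newly suspected to be drug-related. Nothing visible ties RRT records to the laboratory tables.

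A reader might infer that participants on RRT will, as a rule, be tabulated as normal or improving. The documents do not support that: it is a possible result that depends on baseline, on the reason for RRT and on which peaks were recorded. Nor does Table 8-1 contradict the SAP; a staging scale and a table of observed values serve different purposes.

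**Conclusion.** The point holds for the visible safety laboratory tables of SAP 2.6.1 and no further. Followed as written, they can leave a participant who starts RRT out of the creatinine or BUN notable count, and they mix on-RRT with native values in the by-visit creatinine, BUN and potassium summaries.

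The thresholds of about 2.27 mg/dL for creatinine and 56 mg/dL for BUN rest on a Day 1 baseline and on RRT starting at the azotemia criterion. RRT for another reason can be missed at other baselines. Each missed participant is worth 6.7 points on TIN816 or 20 points on placebo.

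How many would be missed cannot be derived from the documents. The 1.5 to 6 of 15 in Step 4 is an assumed number on RRT, not a number missed, and the 0.2 to 0.8 mg/dL shift is an illustration on assumed values. No error rate or power is involved. This is a cheap improvement to how a small descriptive safety table reads, not a flaw in the trial's primary analysis.

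**What to change.** In SAP 2.6.1:

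1. Keep the observed creatinine and BUN notable counts. Add a row by arm for participants with a notable creatinine/BUN value or RRT started after dosing. This reports RRT without recording a 50% rise that nobody measured.
2. Flag creatinine, BUN, potassium and bicarbonate values taken on RRT, using the surgical and medical procedures data already scheduled at each visit. Confirm that these data carry RRT start and stop dates.
3. Show the number on RRT at each visit and in each arm.
4. Present the renal by-visit summaries both with and without on-RRT values, and do not only exclude them.

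The cost is SAP wording, one derived flag and a few table rows. The off-RRT summaries will rest on fewer and less sick participants, so they must be read beside the number on RRT. No change to the protocol's clinical follow-up of renal events is needed.
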